#### Period for Derivation of BOR and PFS

The period is defined from randomization until PD per RECIST v1.1 (Appendix 4 of B9991016 protocol) or death due to any cause.

#### Evaluation of Target Lesions at Each Visit

- The sum of lesion dimensions (SLD) is only considered if the methods of assessments are consistent with baseline. The “interchangeable” methods noted above are all considered consistent methods.
- In the SLD, the longest diameter will be used for non-nodal lesions and the short axis dimension will be used for each lymph node included in the sum.
- Complete Response (CR) is defined by the disappearance of all non-lymph node target lesions (where all target lesions are recorded with a length of 0 mm on the “Target Lesions” eCRF). Any pathological lymph nodes (recorded as target lesion) must have reduction in short axis to <10 mm. Note: the SLD may not be zero if lymph nodes are included as target lesions.
- Partial Response (PR) is defined by a 30% or more decrease in SLD of target lesions, taking as reference the baseline SLD.
- Progressive Disease (PD) is defined by a 20% or more increase in the SLD of target lesions relative to nadir (smallest SLD considering baseline and all assessments prior to the timepoint under evaluation), with a minimum absolute increase of 5 mm relative to nadir.
  - If only a subset of target lesions are assessed and the sum of the non-missing lesion diameters results in an increase above of at least 5 mm and at least 20% above the nadir, then the progression criteria will have been met.
- Stable Disease (SD) is assigned when neither sufficient shrinkage to qualify for CR or PR, nor sufficient increase to qualify for PD is observed, taking as reference the nadir.
- No Target Lesion at Baseline (NB) is assigned if “No Target Lesion” is checked, on the “Target Lesions” eCRF.
- Not All Evaluated (NAE) is assigned if:
  - Any individual target lesion is evaluated as “Indeterminate” on the “Target Lesions” eCRF
  - Inconsistent methods are used for any target lesions after randomization
  - One or more target lesions are not assessed

- One or more target lesions were excised or irradiated and have not reappeared or increased.

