## 5. STUDY TREATMENTS

For the purposes of this study, and per International Conference on Harmonisation (ICH) guidelines, investigational product is defined as a pharmaceutical form of an active ingredient or placebo being tested or used as a reference in a clinical trial, including a product with a marketing authorization when used or assembled (formulated or packaged) in a way different from the approved form, or when used for an unapproved indication, or when used to gain further information about an approved use (ICH E6 1.33).

In this study, the investigational products are all study treatments to be administered, namely, avelumab (MSB0010718C)/placebo and SOC CRT. The study treatments include the following:

- Arm A: Avelumab + SOC CRT:
  - Avelumab 10 mg/kg IV: Day 1 of the Lead-in phase; Days 8, 25, and 39 of the CRT Phase; Q2W for 12 months during the Maintenance Phase.
  - Cisplatin 100 mg/m^2 IV: Days 1, 22, and 43 of the CRT Phase.
  - IMRT 70 Gy/35 fractions/7 weeks; 1 fraction/day, 5 fractions/week for 7 weeks during the CRT Phase.
- Arm B: Placebo + SOC CRT:
  - Placebo IV matching avelumab: Days 1 of the Lead-in phase; Days 8, 25, and 39 of the CRT Phase; Q2W for 12 months during the Maintenance Phase.
  - Cisplatin 100 mg/m^2 IV: Days 1, 22, and 43 of the CRT Phase.
  - IMRT 70 Gy/35 fractions/7 weeks; 1 fraction/day, 5 fractions/week for 7 weeks during the CRT Phase.

Note: The Day 25 dose of avelumab/placebo during the CRT Phase may be administered between Day 24 and Day 29.

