### **5.4. Investigational Product/Study Treatments Supplies**

#### **5.4.1. Radiation Therapy to the Primary Lesion and Neck (IMRT)**

##### **5.4.1.1. Dose Specifications**

Radiation therapy (RT) will be delivered using IMRT technique and will be delivered in 35 fractions over 7 weeks, 5 fractions weekly either in one plan (simultaneous integrated boost [SIB]) or through separate plans, of cone-down boosts. Detailed definitions of clinical target volumes to encompass gross disease with appropriate margin (clinical target volume [CTV]1), high risk sub-clinical disease sites (CTV2) and lower risk areas, as well as normal tissue maximal doses are detailed separately in the Radiation Delivery Guidelines Document.

For questions regarding IMRT, please contact [name] [REDACTED] or call PPD [REDACTED].

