### **5.2.11. Adequate post-baseline tumor assessment**

An adequate post-baseline assessment is defined as an assessment where a response of uCR, uPR, SD, non-uCR/non-PD, or PD can be determined (see Section 6.2.2.8). Time points where the response is not evaluable (NE) or no assessment was performed will not be used for determining the censoring date.

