**Distant metastatic disease** is defined as new tumor identified at a site distant from the head and neck anatomic region or draining lymph nodes. Biopsy of any presumed distant metastatic disease is strongly recommended. A solitary, speculated lung mass/nodule is a second primary neoplasm and is not a disease progression event unless proven otherwise by biopsy in a patient with a smoking history. Multiple lung nodules/masses are considered distant metastases from the index cancer and constitutes a disease progression event unless proven otherwise by biopsy.

Irradiation of the primary tumor and radiographically enlarged lymph nodes is considered part of the treatment under investigation in this clinical trial and therefore these target lesions remain evaluable lesions for response assessment.

It is expected that the status of the primary tumor is assessed thoroughly at the beginning of the surgical procedure before undertaking nodal dissection. Presence of persistent disease at the primary site, confirmed by frozen section will be considered disease progression.

Neck dissection parameters are described in Section 3.4 of the B9991016 protocol and will consist of a selective neck dissection unless a cytologic sampling of the nodes that appear enlarged is negative. Positive neck specimens removed within 140 days after completion of CRT will be considered part of the initial treatment plan and not considered as failures of initial management; positive specimens upon neck dissection beyond 140 days will be considered regional failures.

Progression-Free Survival (PFS) is defined as the time from the date of randomization to the date of the first documentation of PD or death due to any cause, whichever occurs first. For example, the date of first documentation of PD when there is locoregional PD per RECIST v1.1 which is subsequently confirmed by pathology, will be the date of the locoregional PD per RECIST v1.1 rather than the date of pathology confirmation.

PFS data will be censored on the date of the last adequate tumor assessment or clinical evaluation for patients who do not have an event (PD or death); the analysis will consider any PD or death as an event regardless of the number of prior missing tumor assessments or clinical evaluations or timing of the event with respect to initiation of subsequent anti-cancer therapy.

The censoring and event date options to be considered for the PFS and DR analysis are presented in Table 9.

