**Table 13. Outcome and Event Date for PFS Sensitivity Analysis (S0)**

Scenario	Date of event/censoring	Outcome
No adequate baseline assessment and no PD and no death	Date of randomization	Censored
No adequate post-baseline tumor assessment and no death	Date of randomization	Censored
PD or death	Date of PD or death	Event
No PD and no death	Date of last adequate tumor assessment documenting no PD	Censored

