**Table 14. Outcome and Event Date for PFS Sensitivity Analysis (S1)**

Scenario	Date of Progression/Censoring	Outcome
No adequate baseline assessment	Date of randomization a	Censored a
PD or death 
 
- following at most one missing or indeterminate post-baseline tumor assessment, OR
 
- <math>\leq 36</math> weeks after the date of randomization
 
	Date of PD or death	Event
PD or death following two or more missing or indeterminate post-baseline tumor assessments b	Date of last adequate tumor assessment b documenting no PD prior to new anti-cancer therapy or missed assessments	Censored
No PD and no death		
New anti-cancer therapy given		
a If the patient dies $\leq 36$ weeks after start date, the death is an event with date on death date. b If there are no adequate post-baseline tumor assessments prior to the PD or death, then the time without adequate assessment should be measured from the date of randomization; if the criteria were met the censoring will be on the date of randomization		

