**Table 27. Derivation of Objective Status Based on Target and Non-Target Lesion Response Assuming No New Lesions**

Target Lesion Response	Non-Target Lesion Response	Objective Status
CR	CR	CR
CR	Non-CR/Non-PD	PR
CR	PD	PD
CR	NAE	PR
PR	CR	PR
PR	Non-CR/Non-PD	PR
PR	PD	PD
PR	NAE	PR
SD	CR	SD
SD	Non-CR/Non-PD	SD
SD	PD	PD
SD	NAE	SD
PD	Any	PD
NAE	PD	PD
NAE	CR Non-CR/Non-PD NAE	NE
NB	CR	CR
NB	Non-CR/Non-PD	Non-CR/Non-PD
NB	PD	PD
NB	NAE	NE
CR	NB	CR
PR	NB	PR
SD	NB	SD
PD	NB	PD
NAE	NB	NE

CR=Complete Response, PR=Partial Response, SD=Stable Disease, PD=Progressive Disease,  
NAE=Not All Evaluated; NE= Not Evaluable

Note: If non-target (or target) lesions are not collected at baseline, then the overall response is equivalent to the target (or non-target) lesions response, respectively.

If there are any new lesions at a time point, then the response is PD at that time point regardless of target or non-target lesion response.

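### SAP Appendix 3 makes target lesions treated with protocol IMRT non-evaluable, against SAP 6.1.1.1, and as written would distort the standard-RECIST PFS and response analyses

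*SAP*

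**What the plan says.** The evaluability rule appears in two conflicting forms.

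- **Not evaluable.** SAP Appendix 3 (Evaluation of Target Lesions at Each Visit) assigns NAE if "One or more target lesions were excised or irradiated and have not reappeared or increased". Protocol Appendix 4 has the same item in its Indeterminate list for target disease. Neither exempts study radiotherapy.
- **Evaluable.** SAP 6.1.1.1, protocol Section 3.3 and protocol Appendix 3 treat irradiation of the primary tumor and enlarged nodes as part of study treatment and conclude: "therefore these target lesions remain evaluable lesions for response assessment".

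Protocol Section 5 gives both arms "IMRT 70 Gy/35 fractions/7 weeks; 1 fraction/day, 5 fractions/week for 7 weeks during the CRT Phase", and Section 5.4.1 directs it to the primary lesion and neck.

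The SAP uses Appendix 3 for programmatic standard-RECIST BOR, uOR, DR and TTR (Section 6.2.2) and for PFS sensitivity analyses S0 to S4 (Section 6.2.2.2). Section 5.2.11 adds: "Time points where the response is not evaluable (NE) or no assessment was performed will not be used for determining the censoring date". Table 13 (S0) censors at randomization under the row "No adequate post-baseline tumor assessment and no death". Table 14 (S1) also censors "PD or death following two or more missing or indeterminate post-baseline tumor assessments", unless the event falls within 36 weeks of randomization.

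**The concern.** Protocol IMRT covers the primary tumor and neck, where the target lesions of locally advanced disease are expected to lie. Read literally, the NAE item would apply to a responding or stable irradiated target lesion at every visit after radiotherapy. No text says which rule governs the program, and SAP Appendix 3 points its derivation period to protocol Appendix 4, where the same item sits.

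Protocol 9.3.1 commits to a PFS sensitivity analysis with PD per standard RECIST, and S0 is that analysis. Under the literal rule S0 and S1 could fail to support a true PFS effect, and standard-RECIST response would be nearly empty, purely because of a scoring clause. Choosing the reading after unblinding would be open to challenge.

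**Working it through.** **1. The plan's own figure.** Inputs from protocol 9.1: HR 0.68, 1-sided alpha 0.025, 90% power, 1:1 allocation.

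- Schoenfeld events: 4 × (1.960 + 1.282)² / (ln 0.68)² ≈ 283. Freedman's formula gives 290.
- Fixed-design power at 289 events: Φ(0.3857 × √289 / 2 − 1.960) = Φ(1.318) = 0.906.
- Two looks (217 and 289 events, Lan-DeMets O'Brien-Fleming): interim alpha 0.0097, z 2.338, final nominal p 0.0221, power 0.902. The SAP has 0.0097, 2.338, 0.022 and 0.9010.

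The design figures reproduce and are not in dispute. They anchor the illustration below.

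**2. Trace through the SAP for a patient with irradiated target lesions that have not regrown.**

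- Table 27: target NAE with non-target CR, Non-CR/Non-PD, NAE or no non-target lesions gives NE. Only non-target PD (or a new lesion) gives PD. CR, PR and SD cannot be reached.
- Section 5.2.11: an NE visit is not an adequate assessment.
- Table 13: an event-free patient therefore has no adequate post-baseline assessment and is censored at randomization. PD and death still count as events in S0.
- Table 14: the first two visits fall at about week 1 + 7 + 12 = 20 and week 20 + 16 = 36. PD or death after week 36 will usually follow two indeterminate visits, and footnote b then censors it at randomization.

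Patients without target lesions follow the separate rows of Table 27 and are not affected.

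**3. Direct count for S0.** At 289 events, 640 − 289 = 351 patients (55%) are event-free. Multiplying by the assumed share with irradiated target lesions gives 351, 316, 263 or 176 patients censored on day 1 at shares of 100%, 90%, 75% or 50%.

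**4. Simulated effect on S0.** 2,000 trials under the design assumptions:

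- 640 patients; exponential medians 33 and 48.5 months; accrual rising over 22 months.
- Cutoff at the later of 289 events and 24 months after the last patient (mean month 54).
- Visits as in step 2 with their windows; PD dated at the next visit; deaths dated exactly.
- Assumed, not in the documents: dropout spread as 15% over 40 months, 25% of first events are deaths, eight strata with equal hazards, standard-RECIST PD at the time of true PD.
- Stratified Cox and log-rank, single look.

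| Share with irradiated target lesions | S0 HR (true 0.68) | Rejection at 1-sided 0.025 | Ceiling on standard-RECIST uORR |
|---|---|---|---|
| 100% | 0.92 | 10% | 0% |
| 90% | 0.84 | 30% | 10% |
| 75% | 0.78 | 55% | 25% |
| 50% | 0.72 | 76% | 50% |

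With lesions evaluable, rejection is 88–91%. The 36-month PFS estimates (Arm B/Arm A) are 7%/9% at a 100% share and 21%/30% at 75%, against 47%/60% when evaluable. The mechanism is simple: events stay in while event-free follow-up is deleted.

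Varying the death share (10% or 40%), removing dropout, or fixing the cutoff at month 51 gives:

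- HR 0.92–0.94, 0.84–0.85, 0.78 and 0.72–0.73 at the four shares;
- rejection 7–10%, 24–31%, 49–56% and 73–76%.

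A simpler simulation with exact event times gave 0.93 and 9% at a 100% share, 0.79 and 53% at 80%, and 0.74 and 72% at 60%. A further check gave 0.94 and 5% at 100%, and 0.79 and 50% at 75%.

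**5. S1.** Week 36 is 36 × 7 / 30.4375 = 8.28 months. Expected events by then, ignoring dropout:

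320 × [1 − exp(−0.693 × 8.28/33)] + 320 × [1 − exp(−0.693 × 8.28/48.5)] ≈ 51 + 36 = 87 of 289 (30%).

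The simulation keeps 85 events (29%) at a 100% share and 136 (47%) at 75%, with rejection of 2% and 50%. Censoring for new therapy was not modelled.

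**The case against.** The strongest reply is that the documents already settle the matter. The evaluability sentence is specific to this trial and appears three times, whereas the NAE item is generic RECIST wording. The literal reading would also make most of SAP Appendix 3 and Table 27 pointless, so a programmer reading the whole SAP has reason to reject it. No data route is shown either: the item names no eCRF field, IMRT is listed as non-CRF data handled by a central vendor, and Section 6.5.3.3 derives only days, total dose and compliance. S0 to S4 are called purely exploratory, and an error of this size should be conspicuous in the tables.

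Much of this stands as a limit on the consequence. It does not remove the contradiction. Specific-over-general is an inference that the SAP does not state, and ignoring a listed rule would be an undocumented departure from the specification. A data route is also possible, though this too is inference: protocol Appendix 4 calls such target disease Indeterminate, and another NAE item accepts any target lesion marked Indeterminate on the eCRF.

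Confining the evaluability sentence to modified RECIST does not help. Modified RECIST changes only the definition of PD, and protocol 9.3.2.3 defines objective response by CR or PR per Appendix 4.

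It is also fair to note that SAP Appendix 3 drops the protocol's condition that progression has not been documented. For study IMRT this stops mattering once the item is limited. Appendix 3 also lets PD be met on a subset of lesions, and Table 27 carries target PD through to PD.

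**Conclusion.** The concern holds: the rule is wrong as written and should be fixed. Applied literally, it makes CR, PR and SD unattainable for patients with irradiated target lesions. In S0 it censors up to 351 of 640 patients at randomization, and the apparent hazard ratio moves from 0.68 to between 0.72 (50% share) and 0.92 (100% share).

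These sizes rest on two things the documents do not give: the share of patients with irradiated target lesions, and whether the program would apply the item to protocol IMRT. They illustrate literal programming and do not forecast the result. The textual conflict depends on neither.

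Primary PFS events and OS do not use SAP Appendix 3, so the primary conclusion is not at risk. The documents do not show whether the BICR analyses use the same clause. Modified-RECIST response escapes it only if the evaluability sentence governs.

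**What to change.** Before unblinding, amend SAP Appendix 3 in three respects:

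- limit the irradiation part of the NAE item to irradiation other than protocol IMRT;
- carry over the evaluability sentence from SAP 6.1.1.1;
- state that it takes precedence over the matching item in protocol Appendix 4 for S0 to S4 and for the response endpoints, under both programmatic standard RECIST and modified RECIST.

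The cost is one or two SAP sentences and matching programming. No new data are needed. The primary endpoint and its analysis do not change, so the SAP Section 2 condition for a protocol amendment is not triggered.

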#### Evaluation of Non-Target Lesions at Each Visit

The lesions assessed are only considered for CR, Non-CR/Non-PD and PD if the methods of assessments are consistent with baseline. The “interchangeable” methods noted above are all considered consistent methods.

- CR is defined by the complete disappearance of all non-target lesions (where all non-target lesions are marked ‘Absent Lesion or Normal Lymph Node’ on the “Non-Target Lesion” eCRF).
- Non-CR/Non-PD is defined by persistence of one or more non-target lesions (ie, if all non-target lesions are marked ‘Present/Not Increased’ on the “Non-Target Lesion” eCRF).
- PD is assigned if any non-target lesion is marked “Increased” or “Present (First Appearance)” on the “Non-Target Lesion” eCRF.
- No Non-Target Lesion at Baseline (NB) is assigned if “No Non-Target Lesions” is marked on the “Non-Target Lesions” eCRF.
- Not All Evaluated (NAE) is assigned if:
  - Any individual non-target lesion is evaluated as “Indeterminate” (marked as “Indeterminate” on the “Non-Target Lesions” eCRF)
  - Inconsistent methods are used for any non-target lesions after randomization
  - One or more non-target lesions are not assessed.

**New Lesion:** is defined by the appearance of 1 or more new lesions (where any lesion is marked ‘New’ on the “New Measurable Lesions” or “New Non-measurable Lesions” eCRFs). In addition, any lesion that is recorded for the first time after the start date without being marked as “New” on the “New Lesions” eCRF must be queried. In case the inconsistency is not resolved at time of data base snapshot/lock, the lesion will be considered as new and the patient in progression at that time point. Note: the requirement for consistent methods of assessment with baseline, obviously, does not apply for new lesions.

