**NOTE: When nodal lesions decrease to <10 mm (normal), the actual measurement should still be recorded.**

### **Non-Target Disease**

All non-measurable disease is non-target. All measurable lesions not identified as target lesions are also included as non-target disease. Measurements are not required but rather assessments will be expressed as ABSENT, INDETERMINATE, PRESENT/NOT INCREASED, INCREASED. Multiple non-target lesions in one organ may be recorded as a single item on the case report form (eg, 'multiple enlarged pelvic lymph nodes' or 'multiple liver metastases').

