### **Non-Target Disease**

- CR: Disappearance of all non-target lesions and normalization of tumor marker levels. All lymph nodes must be 'normal' in size (<10 mm short axis).
- Non-CR/Non-PD: Persistence of any non-target lesions and/or tumor marker level above the normal limits.
- PD: Unequivocal progression of pre-existing lesions. Generally the overall tumor burden must increase sufficiently to merit discontinuation of therapy. In the presence of SD or PR in target disease, progression due to unequivocal increase in non-target disease should be rare.
- Indeterminate: Progression has not been determined and one or more non-target sites were not assessed or assessment methods were inconsistent with those used at baseline.

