#### Objective Response Status At Each Assessment

- Overall response is determined from the derived target and non-target lesion data using conventions in Table 27 under the assumption that there are no new lesions identified at the visit. **If there are any new lesions at a time point, then the response is PD at that time point regardless of target or non-target lesion response.**
- Objective status after a change in modality that is not considered interchangeable is classified as NE.

- To group target and non-target lesion measurements to the corresponding actual post-baseline tumor assessment visit, a clustering algorithm is applied. Each cluster represents an actual visit. For each patient, the number of clusters is equal to the maximum number of assessments available among all target and non-target lesions. The SAS procedure, Proc Fastclus, is applied to a variable that represents the days from randomization to the date of the scan for lesion (date of scan – randomization +1). Then the assessments of lesions (target, non-target, new) that occurred close to each other in time will be assigned to the same cluster.

The rules for derived objective status for each visit are presented in Table 27.

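### SAP Appendix 3 codes non-target Non-CR/Non-PD as all lesions persisting, against its own definition and protocol Appendix 4, so a partly cleared visit can be left without a category in the standard-RECIST derivation

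*SAP*

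**What the plan says.** SAP Appendix 3, under Evaluation of Non-Target Lesions at Each Visit, sets four categories for assessed non-target disease, plus one (NB) for patients with no such lesions at baseline.

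- CR: "CR is defined by the complete disappearance of all non-target lesions", with every lesion marked as absent or a normal node.
- Non-CR/Non-PD: "Non-CR/Non-PD is defined by persistence of one or more non-target lesions (ie, if all non-target lesions are marked"; the eCRF value required of each is Present/Not Increased.
- PD: "PD is assigned if any non-target lesion is marked" as increased or as a first appearance.
- NAE: a lesion is indeterminate, was assessed by an inconsistent method, or "One or more non-target lesions are not assessed".

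Protocol Appendix 4 defines the middle category as "Non-CR/Non-PD: Persistence of any non-target lesions and/or tumor marker level above the normal limits". It also lists the statuses recorded for non-target disease: "ABSENT, INDETERMINATE, PRESENT/NOT INCREASED, INCREASED".

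The SAP then combines the parts: "Overall response is determined from the derived target and non-target lesion data using conventions in Table 27". New lesions override everything else: "If there are any new lesions at a time point, then the response is PD at that time point regardless of target or non-target lesion".

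**The concern.** The Non-CR/Non-PD sentence gives two rules that cannot both be programmed. The clause before the parenthesis is met by a single persisting lesion. The parenthesis, which is the only part expressed in eCRF values and so the part a programmer is likely to code, is met only if every lesion persists.

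The two rules differ for one kind of visit: some non-target lesions absent, the others unchanged. That is a plausible finding after chemoradiotherapy. Protocol Appendix 4 limits target lesions to 2 per organ and classes nodes with a short axis of 10 to 14.9 mm as non-measurable, hence non-target, so a patient may have several non-target entries.

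The derived status feeds the standard-RECIST versions of best overall response, objective response, duration of response and time to response (SAP 6.2.2). It also feeds PFS sensitivity analysis S0 and its variants S1 to S4 (SAP 6.2.2.2). Under SAP 5.2.11 a visit can set a censoring date only if a response can be determined. A visit that loses its status can therefore lose a response, move a censoring date earlier, or count as indeterminate in S1.

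**Working it through.** The plan states no figure that bears on this point, so the check is logical.

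**Step 1: the mixed visit against each category.** Take two non-target lesions, one absent and one Present/Not Increased, both assessed by a consistent method.

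- CR fails, because not every lesion is absent.
- Non-CR/Non-PD fails under the parenthesis (not every lesion persists) but is met under the definition and under protocol Appendix 4 (one lesion persists).
- PD fails, because no lesion is increased or newly appearing.
- NAE fails, because nothing is indeterminate, unassessed or assessed inconsistently. A lesion recorded as absent has been assessed.

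**Step 2: is this the only gap?** Allow each lesion one of six statuses: absent, Present/Not Increased, increased, first appearance, indeterminate, not assessed. With k lesions there are C(k+5, 5) unordered combinations. Under the parenthesis the unassigned ones are exactly the mixes of absent and Present/Not Increased, so there are k − 1 of them.

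| k | Combinations | Unassigned, parenthesis | Unassigned, definition |
|---|---|---|---|
| 1 | 6 | 0 | 0 |
| 2 | 21 | 1 | 0 |
| 3 | 56 | 2 | 0 |
| 4 | 126 | 3 | 0 |

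These are counts of patterns, not frequencies of visits. For the last column the definition was coded as at least one lesion persisting, all others persisting or absent, and none meeting a PD or NAE criterion.

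**Step 3: pass the mixed visit through Table 27, with no new lesion.**

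| Target response | No category | Non-CR/Non-PD | NAE |
|---|---|---|---|
| CR | no row | PR | PR |
| PR | no row | PR | PR |
| SD | no row | SD | SD |
| PD | PD | PD | PD |
| NAE | no row | NE | NE |
| No target lesion (NB) | no row | Non-CR/Non-PD | NE |

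Without a category there is no row for 5 of the 6 target responses. The last two columns differ only in the NB row.

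**Step 4: what follows from each way of coding it.**

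- *Definition coded:* no gap, and agreement with the protocol.
- *Parenthesis coded, with NAE as fallback:* only patients without target lesions change. Their visit becomes NE, so it is no longer an adequate assessment under SAP 5.2.11. Best overall response may fall from Non-CR/Non-PD to NE, and a censoring date may move earlier. Objective response at that visit does not change, since Non-CR/Non-PD is not a response.
- *Parenthesis coded, category left blank:* a PR (target CR or PR) or SD (target SD) can be lost as well. In S0 an event-free patient can be censored earlier, while PD and deaths remain events. In S1 (SAP Table 14) two or more such visits before PD or death, if read as missing or indeterminate, can turn an event into a censoring unless it falls within 36 weeks of randomization.

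**The case against.** The strongest reply is that the definition governs and the parenthesis is a slip. The definition and protocol Appendix 4 both classify the mixed visit, and Appendix 3 refers to that protocol appendix for its derivation period. On that reading the plan does have a category for the visit. This stands: the defect is a definition contradicted by its own coding rule, not a missing concept.

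A reader might infer that every partly cleared visit ends with no objective status. The documents do not support that. Target PD gives PD whatever the non-target category, and so does a new lesion.

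A reader might also infer that true partial responses would routinely be lost. That does not follow either. For target CR, PR, SD or NAE, Table 27 gives the same status under NAE as under Non-CR/Non-PD. The response table in protocol Appendix 4 likewise gives PR, PR and SD for target CR, PR and SD when non-target response is missing. A lost PR needs a program that leaves the category blank and then discards the target response, which neither table prescribes.

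It is also fair that the SAP calls the PFS sensitivity analyses exploratory, that the rule applies alike to both arms of a blinded trial, and that no directional bias has been shown.

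What the reply does not remove is the conflict itself. The parenthesis is wrong as written, the SAP names no fallback, and two programmers could produce different datasets from the same sentence.

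**Conclusion.** The point holds as an internal contradiction in a derivation rule. Its consequences are conditional: none if the definition is coded, limited to patients without target lesions if NAE is the fallback, and wider only if the category is left blank.

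Its scope is the programmatically derived standard-RECIST analyses: S0 to S4 and the standard-RECIST best overall response, objective response, duration of response and time to response. Primary PFS rests on investigator assessment per modified RECIST (SAP 6.1.1.1), and S0_B and M1_B rest on central review. None of these uses the rule, so a reader should not infer a threat to the primary result.

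The size cannot be estimated from the documents. One could assume that each of k lesions clears independently with probability p and compute the chance of a mixed visit as 1 − p^k − (1 − p)^k. For p from 0.5 to 0.8 this runs from 0.32 (k = 2, p = 0.8) to 0.88 (k = 4, p = 0.5). That range should not be read as the share of visits lost. Neither p, k nor independence comes from the plan. Lesions in one patient share the same treatment, and positive correlation would lower the figure. Protocol Appendix 4 allows several non-target lesions in one organ to be recorded as a single entry, which reduces k, and with k = 1 there is no gap. A mixed visit is also not a lost visit unless the blank-category coding applies.

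**What to change.** In SAP Appendix 3, replace the parenthesis after the Non-CR/Non-PD definition with: (ie, at least one non-target lesion is marked Present/Not Increased, all others are marked Present/Not Increased or Absent Lesion or Normal Lymph Node, and no PD or NAE criterion is met).

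This matches the definition beside it and protocol Appendix 4, and every combination in the enumeration then has a category. Table 27 needs no change.

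The cost is one SAP sentence and one program condition, best settled before database lock. If the derivation is already programmed, check which of the two rules was coded and what happens to a visit that meets none of the categories.
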